# Clinical Investigation Plan (CIP)

Study Name: VivaSight-DL study (CIS-009)  
Ethical committee number: S-20180081

CLI-000427

Rev. 02

- Number of intubation attempts
  - Intubation attempt is defined as the number of intubation attempts until successful intubation is accomplished. If the endotracheal tube is incorrectly placed and the tube is withdrawn from the subjects throat it counts as one attempt.
  - If more than three intubation attempts are used the intubation is defined as a failure and the subject is excluded from the study.
- Number of times incorrect placement of the tube is prevented during intubation
  - Prevention of repositioning is a corrective action that ensures optimal ventilation of the subject without having to move the tube after the bronchial cuff is inflated. An example of a corrective action during intubation could be change of the tube direction if it starts to enter the right main bronchi instead of the left main bronchi when advanced down the throat.
- Number of times the tube needs to be repositioned during intubation
  - In this study, repositioning is defined as the action where the bronchial cuff needs to be deflated to move the tube into the right position.
- Number of times where the physician prevents repositioning of the tube during surgery
  - Prevention of repositioning is a corrective action that ensures optimal ventilation of the subject without having to move the tube after the bronchial cuff is inflated. An example of a corrective action during surgery could be optimization of the cuff sealing by deflating and inflating the cuff without moving the tube.
- Number of times the tube needs to be repositioned during surgery.
  - In this study, repositioning is defined as the action where the bronchial cuff needs to be deflated to move the tube into the right position.
- Repositioning time (seconds) during surgery
  - In this study, repositioning is defined as the action where the bronchial cuff needs to be deflated to move the tube into the right position.
  - Time starts: when the syringe is attached to the valve to deflate the bronchial cuff
  - Time stops: when correct bronchial cuff placement is verified by capnography
- Rate of restriction on the surgical procedure during repositioning of the tube
  - One of the following statements is chosen:
    - Not restricted
      - The surgical procedure is not restricted at all, the surgeon continues to work full speed
    - Restricted

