## 6.2 Exclusion criteria for subjects

- Subjects with known tracheobronchial anatomic anomalies
- Subjects going for emergency procedures
- Subjects with anticipated difficult airways
- Subjects with known tracheal pathology
- Subjects requiring rapid sequence induction
- Surgeries in which other lung isolation devices or techniques may be warranted (e.g. tracheostomy, nasal intubation, bronchial blockers)
- Subjects who cannot be intubated with a double-lumen tube (VivaSight-DL or conventional DLT)
- Subjects requiring a right-sided DLT
- Subjects who had participated in the study before

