## 6.5 Exclusion during the examination

The subject can be excluded during the investigation if:

- The subject or legal representative decides to abort the study
- The subject is assigned to a physician with experience in > 50 DLT intubations in patients
- The investigator considers it necessary to change the type of endotracheal tube used for the procedure
- The investigator assess that it is necessary to exclude the subject from the investigation to ensure safety of the subject

If a subject withdraw from the study before the study randomization envelopes seal is broken (example no. 10), then the next subject will continue with consecutive subject number (no. 11).

If the subject is excluded *after* the procedure is started, he or she will be treated and receive routine treatment. Reason for exclusion will be stated in the CRF but otherwise data will not be collected in the CRF.

If the subject is excluded *before* the procedure is started, he or she will receive routine treatment. Reasons for exclusion will be stated in the CRF but otherwise data will not be collected in the CRF.

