## 7.3 Preparation of the procedure

Latest on the day of the procedure, the subject will be assigned a physician who will perform the intubation. If the subject is assigned a physician with experience in > 50 DLT intubations in patients, the subject will be excluded from the study and receive the standard treatment. If the subject is assigned a physician with experience in < 50 DLT intubations, the subject will be randomized to receive single-lung ventilation using either VivaSight-DL (test group) or Shiley™ Endobronchial Tube (control group).

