### 7.5.1 Intubation technique with VivaSight-DL

1. Lubricate the tube (if needed), avoiding the area around the camera lens at the distal end of VivaSight-DL.
2. Introduce the direct laryngoscope into the subject's mouth
  - *Start recording the "Intubation time"*
3. VivaSight-DL is introduced into the subject's mouth
  - *A maximum of 3 intubation attempts, the number of intubation attempts are recorded in the CRF*
4. Advance the VivaSight-DL bronchial tube through the vocal cords with the tip facing upward and remove the stylet.
5. At the proximal portion of the tube, the bronchial arm of the tube will be positioned above the tracheal arm.
6. When the tip passes the vocal cords, and before the camera passes it, turn the tube 90 degrees counterclockwise until the camera on the tube is facing up pointing towards the vocal cords. In this position, the tube passes through the vocal cords with the camera on the superior portion of the tube.
7. When the camera passes the vocal cords, advance the tube further until final positioning (2-3 cm above the main carina), without additional tube maneuvering. When the tube is in place, the proximal portion of the bronchial arm will be horizontal and on the left side.
  - *If any corrective actions are done to prevent repositioning of the tube after the cuffs are inflated it must be recorded in the CRF.*
8. Inflate tracheal cuff.
9. Remove the syringe from valve.
10. Promptly connect the tube to source of ventilation and confirm correct tube placement by capnography (CO2 return)
11. Confirm correct tube position by looking at the aView monitor.
  - *If fiberoptic bronchoscopy is needed to confirm position, the number of times the fiberoptic bronchoscope (FOB) is used must be recorded in the CRF:*
    - Apply lubrication and antifogging agents to the FOB if needed.
    - The FOB is placed through the tracheal lumen.
    - The FOB is advanced, and the carina is identified.
    - The bronchial lumen of the tube must be visualized entering the left main stem bronchus.
12. The bronchial cuff is inflated under direct vision and should lie just distal to the carina.
  - *If the tube needs to be repositioned (bronchial cuff is deflated, and the tube is moved) it must be recorded in the CRF.*
    - *If fiberoptic bronchoscopy is needed to reconfirm position, the number of times the fiberoptic bronchoscope (FOB) is used must be recorded in the CRF:*

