#### 18.3.2 Handling of dropouts and missing data

Data from intermediate dropouts, who has been intubated but not undergone surgery will not be included within the analysis of the primary outcome. Furthermore, data from intermediate dropouts will be included until dropout. Early dropouts, who dropout prior to intubation will be excluded from all analysis.

Potential missing data points will be explored and substituted via regression imputation or listwise deletion as appropriate. Using substitutions via regression imputation the existing variables are used to make predictions for the missing values. As a result, the data is retained, and significant altering of the standard deviation is avoided. To examine whether potential missing data points are missing at random, or whether they could lead to a potential bias, an independent sample t-test will be applied, comparing the remaining variables of the observations with full data and the observations with missing data.

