### Secondary outcomes:

- Intubation time (sec)
  - If the observations are normally distributed, a student t-test will be used to examine if intubation time (sec) is significantly different for procedures using VivaSight-DLT compared to a conventional DLT. If the data is not normally distributed, transformation will be attempted to normalize the data. If the observations are still not normally distributed, a Mann-Whitney U test will be used.
- Number of intubation attempts
  - If the observations are normally distributed, a student t-test will be used to examine if number of intubation attempts is significantly different for procedures using VivaSight-DLT compared to a conventional DLT. If the observations are not normally distributed, a Mann-Whitney U test will be used.
- Number of times incorrect placement of the tube is prevented during intubation
  - If the observations are normally distributed, a student t-test will be used to examine if number of intubation attempts is significantly different for procedures using VivaSight-DLT compared to a conventional DLT. If the observations are not normally distributed, a Mann-Whitney U test will be used.
- Number of times the tube needs to be repositioned during intubation
  - If the observations are normally distributed, a student t-test will be used to examine if number of times the surgeon asked the tube placement to be confirmed is significantly different for procedures using VivaSight-DLT compared to a conventional DLT. If the observations are not normally distributed, a Mann-Whitney U test will be used.
- Number of times where the physician prevents repositioning of the tube during surgery
  - If the observations are normally distributed, a student t-test will be used to examine if number of intubation attempts is significantly different for procedures using VivaSight-DLT compared to a conventional DLT. If the observations are not normally distributed, a Mann-Whitney U test will be used.
- Number of times the tube needs to be repositioned during surgery
  - If the observations are normally distributed, a student t-test will be used to examine if number of times the surgeon asked the tube placement to be confirmed is significantly different for procedures using VivaSight-DLT compared to a conventional DLT. If the observations are not normally distributed, a Mann-Whitney U test will be used.
- Repositioning time (seconds) during surgery

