## 18.5 Pass/fail criteria

All patients included in the results must fulfill the inclusion and exclusion criterion.

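### Failed intubations are excluded after randomisation, so the comparison of intubation attempts covers successes only and can be biased if failures occur

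*Combined protocol and SAP*

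**What the plan says.** - **Endpoint and failure rule (section 4, secondary end-points).** Attempts are counted up to successful placement. The same entry adds: "If more than three intubation attempts are used the intubation is defined as a failure and the subject is excluded from the study".
- **Timing (7.3).** Randomisation takes place during preparation, once a novice physician has been assigned and before anaesthesia and intubation.
- **Data after exclusion (6.5).** For a subject excluded after the procedure has started: "Reason for exclusion will be stated in the CRF but otherwise data will not be collected in the CRF".
- **Recording during intubation (7.5.1 and 7.5.2, both devices).** "A maximum of 3 intubation attempts, the number of intubation attempts are recorded in the CRF". The CRF in Appendix V has a field for the number of attempts but no box for success or failure.
- **Dropouts (18.3.2).** Data up to dropout are kept for one group, described as "Data from intermediate dropouts, who has been intubated but not undergone surgery".
- **Analysis (18.3.3).** A t-test, or a Mann-Whitney test if the data are not normal, is used to "examine if number of intubation attempts is significantly different for procedures using VivaSight-DLT compared to a conventional DLT". The plan gives failures no score and does not plan to compare failures by arm.

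**The concern.** The exclusion comes after randomisation and depends on the outcome being compared. A subject with a failed intubation has the worst possible result on this endpoint, and that is the subject who leaves. The arms that remain are no longer the arms that were randomised. If one device fails more often, its worst results are missing and its mean among the remaining subjects can look better than it should.

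This could work in either direction. If VivaSight-DL is the better device, the rule hides part of its advantage. If it fails more often, the rule flatters it. If 6.5 is followed literally, the attempts count for a failure is not available later, so the analysis could not repair the loss.

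What is at stake is one secondary comparison. The primary endpoint's definition and the sample size are not disputed here.

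**Working it through.** **1. The plan's own figure.** The plan gives no number for this endpoint. Its only calculation is the sample size for the primary endpoint (18.1), and it reproduces: (0.23622 + 0.01087) × (1.96 + 1.28)² / (0.37234 − 0.01087)² = 19.852 per arm, so 40 in total, and 40 / 0.80 = 50.

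**2. Following one failed intubation through the text.** The subject is randomised (7.3). Three attempts are made and none succeeds. Section 4 excludes the subject. Section 6.5 keeps the reason and nothing else, whereas 7.5.1 and 7.5.2 would already have had the count written down. Section 18.3.2 keeps data for subjects who have been intubated, and a failed intubation does not clearly fit that description. Section 4 counts attempts up to success, so no value is defined for a failure. The result is that 18.3.3 compares successes only.

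The threshold is also worded in two ways. Section 4 speaks of more than three attempts, while 7.5.1 and 7.5.2 allow at most three. The intent is evident, but the two should match.

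**3. How many subjects (assumption: independent attempts, each failing with probability q).** Failure after three attempts has probability q³.
- q = 0.10: 50 × 0.001 = 0.05 expected failures; chance of at least one = 1 − 0.999^50 = 5%.
- q = 0.30: 50 × 0.027 = 1.35 expected failures; chance of at least one = 1 − 0.973^50 = 75%.

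**4. Shift in an arm's mean.** Let f be the failure rate, S the score given to a failure and m the mean among successes. With failures kept, the mean is (1 − f)m + fS. With failures excluded, it is m. Exclusion lowers the mean by f(S − m).

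**5. Expected difference between arms, with S = 3.** With failures kept, the mean is (1 − q)(1 + 2q) + 3q². With failures excluded, it is (1 − q)(1 + 2q + 3q²) / (1 − q³).

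| q | f = q³ | Mean, kept | Mean, excluded |
|---|---|---|---|
| 0.10 | 0.001 | 1.110 | 1.108 |
| 0.30 | 0.027 | 1.390 | 1.345 |
| Difference | | 0.280 | 0.237 |

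The ratio is 0.237 / 0.280 = 0.85, so exclusion makes the difference 15% smaller. At 10% against 20%, the difference is 0.130 kept and 0.118 excluded.

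**6. One failure in a trial of 25 per arm (assumed counts, direction only).** VivaSight-DL: 20 subjects with one attempt, 4 with two, 1 with three (31/25 = 1.24). Control: 17, 4 and 4 (37/25 = 1.48). The p-values are from a two-sided Mann-Whitney test with tie and continuity correction.

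| Handling | Difference in means | p |
|---|---|---|
| Failure kept as 3 | 0.24 | 0.28 |
| Failure in control, excluded | 34/24 − 1.24 = 0.18 | 0.41 |
| Failure in VivaSight-DL, excluded | 1.48 − 28/24 = 0.31 | 0.15 |
| Failure in control, ranked worst | not applicable | 0.27 |
| Failure in VivaSight-DL, ranked worst | not applicable | 0.30 |

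None of these crosses 0.05. Ranking a failure worst gives nearly the same p-value as entering 3, so what matters is keeping the subject.

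**7. When it would matter more (failures scored 4).** Suppose both arms have the same distribution among successes, with mean 1.25, and only one arm has failures, at 8%. The plan's comparison has an expected difference of zero, while the difference with failures kept is 0.08 × (4 − 1.25) = 0.22. With per-attempt success of 0.9 against 0.7 (2.7% failures in the worse arm), simulated Mann-Whitney power at 25 per arm is about 45% with failures kept and 37% with failures excluded.

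**The case against.** The best defence is that this may never arise. Section 6.2 excludes anticipated difficult airways, anatomic anomalies, tracheal pathology and rapid sequence induction, and operators first complete at least 13 manikin placements (6.3). The 10% to 30% range and the independence of attempts are assumptions. At the low end there is a 95% chance of no failure in 50 subjects. This stands, and it limits the size of the point. It does not remove the rule.

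Three stronger readings are tempting, and the documents do not support them.

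- **The bias always favours the device that fails more, and vanishes if failure rates are equal.** This is not general, because f(S − m) also depends on m. With S = 3, an arm with f = 5% and m = 2 shifts by 0.050, while an arm with f = 4% and m = 1.1 shifts by 0.076. The device that fails less gains more. This is a constructed case, but it rules out an unconditional statement.
- **The attempts count is certainly lost.** Sections 7.5.1 and 7.5.2 have it recorded during intubation, and 6.5 can be read as stopping only further collection. The sections conflict. The randomised arm and the reason for exclusion are also on the CRF, so failures could probably be counted by arm, although no such summary is planned.
- **A failure also breaches eligibility.** Section 6.2 excludes subjects who cannot be intubated with a double-lumen tube, and 18.5 says "All patients included in the results must fulfill the inclusion and exclusion criterion". But 6.4 has eligibility checked at inclusion, and nothing tells staff to apply the criterion afterwards.

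It is also fair to say that worst rank is one choice among several, and that the repair below covers one endpoint. Exclusion from the study would also take the subject out of intubation time and the bronchoscope count. No size is claimed for either here.

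**Conclusion.** The point holds in conditional form. A stated rule, applied after randomisation, restricts the attempts comparison to successful intubations, and no other section clearly reverses it. If failures occur, the comparison can be biased, typically towards the device that fails more often.

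The size is unknown because the documents give no failure rate. At about 1% failures or fewer it is negligible. Under the assumed contrast of 10% against 30% per-attempt failure, the difference of 0.28 shrinks to 0.24. These figures rest on independent attempts and on scoring a failure as 3.

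This affects one secondary endpoint and should be corrected, because an unknown failure rate is a reason to settle the handling in advance and the correction is cheap.

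**What to change.** - **Section 4:** define failure as no successful placement within three attempts, matching 7.5.1 and 7.5.2. State that for this endpoint the subject stays in the analysis in the randomised arm.
- **Section 6.5 and the CRF (Appendix V):** add a success yes/no box beside the attempts count, and state that both are completed even if the subject is then excluded.
- **Section 18.3.3:** rank failures worse than any success in the Mann-Whitney test, and report the number of failures by arm.

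The cost is a few sentences and one tick box, with no added procedure for the subject. The small downside is that this replaces section 4's exclusion of failures for this endpoint.

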## Tertiary end-points:

- Qualitative measures (questions to the subject) (appendix V)
  - Any side effects from the surgery
  - Daily function level prior surgery
- Qualitative measures (questions to the person who intubates) (appendix VI)
  - Ease of tube placement (very easy, easy, acceptable, difficult, very difficult)
  - How would you rate the overall perception of quality and functionality of the tube (VivaSight-DL or conventional DLT)? (Very poor, poor, acceptable, good, very good)
  - Would you prefer to use VivaSight-DL or conventional DLT in the future (VivaSight-DL/conventional DLT)

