## 7.2 Recruitment of subject

Patient Information will be given during the preoperative visit with the anesthesiologist prior to the surgery. Subjects will be recruited, and Informed Consent will be obtained as described in section 6.4 and 12. After signing the informed consent, the subject is enrolled in the study. The investigator who obtained Informed Consent will write his/her name under “Centre Identification” and “Investigator’s name” and collect the following demographic data, airway assessment parameters and surgical information’s in the CRF under “Patient Information”:

- Age
- Gender
- Height
- Weight
- ASA class
- Indication for the surgery
- Date of enrolment
- Fulfilment of the inclusion/exclusion criteria

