### 7.9 Awakening of subject and follow up

Immediately after the surgery, the physician is asked to complete a questionnaire regarding the procedure just performed (Appendix VI).

All subjects are woken up immediately after surgery. Within forty-eight hours after the surgery, the subject will be contacted (in the hospital room or over the phone) by a research assistant who will ask questions regarding the subject's health-related life quality and potential side effects from the intubation (Appendix V). It will be the same research assistant who contacts all subjects in order to ensure identical data collection across subjects.

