## APPENDIX VI: QUESTIONNAIRE FOR SUBJECTS

### Spørgeskema omhandlende helbredsrelateret livskvalitet og bivirkninger efter operation i hjerte-lunge området

I forbindelse med at De har deltaget i et forskningsstudie og har fået foretaget en operation med behov sikring af dine luftvejene på Odense universitetshospital, vil vi bede Dem besvare nedenstående spørgeskema omhandlende din generelle helbredsrelaterede livskvalitet samt eventuelle bivirkninger efter din operation.

Forsøgsperson nummer: \_\_\_\_\_

Dato for udfyldelse: \_\_\_\_\_

Tidspunkt for udfyldelse: \_\_\_\_\_

Spørgsmål omhandlende helbredsrelaterede livskvalitet						Kommentarer
Hvordan vil De vurdere Deres overordnet livskvalitet indenfor de sidste 4 uger?	 Dårlig	 Mindre god	 God	 Meget god	 Fremragende	
I hvor høj grad har De haft smerter indenfor de sidste 4 uger?	 Slet ikke	 I mindre grad	 I nogen grad	 I høj grad	 I meget høj grad	
I hvor høj grad har Deres smerter påvirket Deres hverdag?	 Slet ikke	 I mindre grad	 I nogen grad	 I høj grad	 I meget høj grad	
I hvor høj grad har De følt dem ængstelig eller deprimeret indenfor de sidste 4 uger?	 Slet ikke	 I mindre grad	 I nogen grad	 I høj grad	 I meget høj grad	
Hvordan vil De vurdere Deres helbred alt i alt?	 Dårligt	 Mindre godt	 Godt	 Meget godt	 Fremragende	
Spørgsmål omhandlende eventuelle bivirkninger efter operationen						Kommentarer
Hvor mange timer er der gået siden Deres operation?	 0-4	 5-9	 10-14	 15-19	 Over 20	
Har De tidligere fået foretaget en lignende operation?	 Ja	 Nej				
Har De oplevet hoste efter Deres operation?	 Ja	 Nej				

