Hvis ja, i hvor høj grad har De hostet?	 Mild	 Moderat	 Svær			
Har De oplevet hæshed efter Deres operation?	 Ja	 Nej				
Hvis ja, i hvor høj grad har De været hæs?	 Mild	 Moderat	 Svær			
Har De haft smerter i svælget efter Deres operation?	 Ja	 Nej				
Hvis ja, hvordan vil De beskrive Deres smerter?	 Milde	 Moderate	 Svære			
Hvis spørgeskema ikke besvares, begrundes dette her:						

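### Cough, hoarseness and throat pain are reported as side effects without any record of whether they were present before surgery, so existing symptoms cannot be told apart from new ones.

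*Combined protocol and SAP*

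**What the plan says.** Section 4 lists "Any side effects from the surgery" among the tertiary end-points. Section 7.9 gives the timing: "Within forty-eight hours after the surgery, the subject will be contacted". One research assistant contacts all subjects.

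The questionnaire in Appendix VI (in Danish) has three symptom items, each answered yes or no and graded mild, moderate or severe if yes:

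- Cough: "Har De oplevet hoste efter Deres operation"
- Hoarseness: "Har De oplevet hæshed efter Deres operation"
- Throat pain: "Har De haft smerter i svælget efter Deres operation"

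Each asks only about the time after the operation. The nearest look-back item is general pain, "I hvor høj grad har De haft smerter indenfor de sidste 4 uger" (pain in the last four weeks). The others cover quality of life, anxiety or depression, and overall health. All are asked after surgery.

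At enrolment, section 7.2 has the investigator "collect the following demographic data, airway assessment parameters" and surgical information. The list that follows is age, gender, height, weight, ASA class, indication, enrolment date and eligibility. The CRF has no further preoperative symptom field. It records cough and throat-pain complaint at extubation (section 7.8).

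Section 18.3.3 plans frequency tables and regression as suitable for side effects, and a chi-square test between arms for the qualitative measures. It names no baseline covariate.

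**The concern.** The end-point claims attribution to the surgery, but the questions measure only presence afterwards. A subject who coughed before the operation and still coughs can truthfully answer yes and be tabulated as having a side effect. The eligibility criteria exclude known tracheal pathology and anatomic anomalies, but not existing cough, hoarseness or sore throat.

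Three things are at stake. The reported side-effect rates may be too high in both arms. The difference between the tubes may be pulled towards zero, which in a harm comparison favours a finding of no difference. And with 25 per arm, a chance imbalance in existing symptoms could pass for a device effect, with nothing recorded that would reveal it or allow adjustment. None of this can be repaired after surgery except by recall.

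**Working it through.** **The plan's own figure.** The only power calculation (section 18.1) is for bronchoscope use: (0.23622 + 0.01087) × (1.96 + 1.28)² / (0.37234 − 0.01087)² = 19.852 per arm, so 39.70, rounded to 40, and 40 / (1 − 0.20) = 50. It reproduces, but has no bearing on side effects, for which the plan states no figure.

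**Where a preoperative value could come from.**

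| Source | Timing | Cough, hoarseness or throat pain before surgery? |
|---|---|---|
| Section 7.2 list and CRF demographics/eligibility block | Before surgery | No |
| CRF extubation fields (section 7.8) | After tube exposure | No |
| Appendix VI symptom items | After surgery | No |
| Appendix VI four-week items | Asked after surgery | No; general pain only |

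**Effect on the comparison.** Let b be the share in each arm with the symptom beforehand and q the new-onset rate among the rest. If every existing case answers yes:

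- observed rate = b + (1 − b)q
- observed difference = (1 − b)(q₁ − q₂)

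**Illustration.** Assumed: q = 50% v 15%, and b = 0, 20% or 40%. From the plan: 25 per arm and two-sided 5%. Power is by exact enumeration of two binomials with an uncorrected chi-square test.

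| b | Observed rates | Difference | Power, as planned | Power, new-onset only, all 25 | Power, symptom-free subjects only |
|---|---|---|---|---|---|
| 0 | 50% v 15% | 35 points | 79% | 79% | 79% |
| 20% | 60% v 32% | 28 points | 56% | 65% | 69% |
| 40% | 70% v 49% | 21 points | 36% | 50% | 56% |

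The new-onset column uses rates (1 − b)q, that is 40% v 12% and 30% v 9%. The difference over all subjects is still 28 or 21 points. The gain is that the rates mean what they say and the noise from existing cases is gone. The full 35 points return only among symptom-free subjects, whose numbers are taken as binomial(25, 1 − b) in each arm.

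**Multiplicity.** Section 18.3.4 applies a Bonferroni correction to exploratory analyses without giving a divisor. If it covers these tests with a divisor of three (assumed, one per symptom), α = 0.05 / 3 = 0.0167. Power as planned then becomes 62%, 34% and 18%.

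**Chance imbalance.** With two independent binomial(25, b) counts, the number of subjects with the symptom beforehand differs between arms by at least 3 with probability 37% at b = 20% and 47% at b = 40%. It differs by at least 5 with probability 11% and 19%.

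**The case against.** The strongest reply is that the harm is conditional and the end-point minor. The items sit under a heading on possible side effects and ask about the time after the operation. One assistant asks them of everyone, and there is a comments column. Some subjects will report only new symptoms, and the severity grade partly separates cases. This stands: full misclassification is an upper bound, and the documents give no prevalence for any of the three symptoms. It does not supply the missing baseline, because subjects who read the question differently give answers that are not comparable.

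It is also fair that the comparison is weak chiefly because 25 per arm was sized for bronchoscope use, and weaker still if Bonferroni applies. That stands too. The missing baseline adds to the weakness but does not cause it.

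Three stronger readings are tempting and unsupported:

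- A reader might infer a bias towards one tube. Randomisation balances existing symptoms in expectation, so what remains is attenuation and chance imbalance.
- A reader might infer that the questionnaire is the trial's only patient-reported airway harm comparison. Throat-pain complaint is also recorded at extubation, for both arms.
- A reader might infer that the main conclusions are affected. Side effects are tertiary and are not among the effect measures of the cost-effectiveness model in section 18.7.

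**Conclusion.** The gap is real: no document records cough, hoarseness or throat pain before tube exposure, so the planned analysis cannot separate existing symptoms from side effects. Its size is unknown. It depends on the share with existing symptoms and on how many of them answer yes, and the documents give neither. If all answer yes, a 20% share cuts the observed difference by a fifth and a 40% share by two fifths. Under the assumed 50% v 15% and an unadjusted 5% test, power falls from 79% to 56% or 36%, and it is lower in every case if the Bonferroni rule applies. This is a worthwhile low-priority improvement, not a threat to the trial's primary or economic findings.

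**What to change.** - **Section 7.2 and CRF baseline block:** at the existing preoperative visit, before the envelope is opened, record the same three symptom and severity items, worded for the time before surgery.
- **Section 4 and Appendix VI:** define a side effect as a symptom that is new, or worse in severity than before surgery.
- **Section 18.3.3:** use that definition as the outcome, and show results by baseline status so that symptom-free subjects can be read separately. Do not simply add baseline presence as a covariate while keeping any symptom as the outcome. If all subjects with the symptom beforehand answer yes, the covariate predicts their outcome perfectly, and at 25 per arm the regression runs into quasi-separation.
- **Section 18.3.4:** state whether the Bonferroni correction covers these tests and with what divisor.

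The cost is about a minute per subject, a few CRF fields and a small amendment. No extra visit, staff or procedure is needed.
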